## 1. Study Protocol

Potential participants were Veterans with recurrent binge eating seeking weight loss were recruited from VA's Weight Management Program, MOVE! at two VA sites: West Haven, CT and Northampton, MA between January 2018 and May 2022. As recruitment for this study was underway during the COVID-19 pandemic, Veterans were first recruited from in-person MOVE! orientation sessions between January 2018 and March 2020 and then additionally from VA's remote TeleMOVE! program starting in July 2020. Eligibility required age 21+, Body Mass Index (BMI) $\geq$ 25, and DSM-5 clinical/subclinical BED. Exclusions were: attendance of more than 4 MOVE! group sessions in the prior year, active psychosis or suicidal ideation, medical or psychiatric illness or cognitive deficits that interfere with providing consent or completing assessments, and pregnancy or lactation. The study received IRB approval by the VA Connecticut Healthcare System, which provides oversight for both West Haven, CT, and Northampton, MA facilities.

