### 1.1 Measures

Participant assessments were conducted by blind assessors at baseline, post-treatment (3-months), and 6- and 12-month follow-ups (9- and 15-months after randomization). Primary outcomes included eating pathology and binge eating, secondary outcomes included measures of mental health, quality of life, and other eating behavior. Weight outcomes were explored. Participants were compensated \$25 for baseline, \$40 for post-treatment, and \$50 and then \$60 for follow-up assessments.

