### 1.2 Diagnostic and Primary Outcomes: Eating Pathology and Binge Eating

Eating Disorder Examination-Interview 17.0th Edition (EDE)[1] is the structured diagnostic interview that is considered the gold-standard to diagnose, and assess the symptoms of, eating disorders including binge eating and eating disorder pathology. Binge Frequency was defined as the average number of monthly binge episodes for the past three months at baseline, and average number of monthly binge episodes for the past month at post-treatment and follow-up assessments. Binge Remission was defined as zero binge episodes in the previous month.

Eating Disorder Examination-Self-report Questionnaire (EDE-Q)[2] is the self-report version of the more intensive EDE interview. Research has documented that the EDE-Q performs well as a measure of change in treatment trials[3] and has adequate convergence with the interview format[4, 5]. The EDE-Q generates the same frequency data for binge eating in the past 28 days, as well as a total score for overall eating pathology and subscale scores for dietary restraint, weight concern and shape concern, and eating concern.

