### *1.6 Randomization*

Stratified randomization (clinical BED (n=101) and subclinical BED (n=8)) to the two conditions was performed with a computer-generated sequence.

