## 2. Statistical Analysis Plan

Baseline characteristics were compared between the treatment groups using ANOVA and chi-squares as appropriate in order to determine the level of success of the randomization. Distributions of outcomes were examined to determine if assumptions of specific model types were met. Change of model type as well as transformation of the data were considered if model assumptions were not met. Mixed-effects models, a method for statistical modeling that uses both fixed effects and random effects, were used to examine continuous outcomes such as eating pathology binge eating frequency, mental health symptoms, and percent weight loss for completer, as well as intent-to-treat (all randomized persons), analyses. Logistic regression models were used for categorical outcomes such as binge remission and achieving clinically meaningful weight loss (i.e., 5% weight loss or greater). The outcomes were transformed to approach normality as needed and models controlled for treatment, time, gender, age, and baseline BMI.

*2.1 Cohort (in-person vs remote) analyses.* There were 40 (37%) subjects in cohort 1 and 69 (63%) in cohort 2. All the analyses with cohort (categorical variable) added to the models were run and conclusions were substantively the same.

*2.2 Missing Data.* Missing data was minimized by having participants complete with assistance of research assistants. The mixed-effects models addressed missing data for continuous outcomes as the modeling makes use of all available data for each participant, even when there are different numbers of observations. [79]

*2.3 Missingness analyses.* We focused on the missingness of the primary outcome averages binge per month (over past 3 months). Outcome was missing for 11.9% of subjects at month 3, 19.3% at month 9, and 24.8% at month 15. Overall, these 3 timepoints, 35.8% of subjects had incomplete outcome data (missing outcome at any of timepoints). There was no evidence of a difference between groups in missingness at any timepoint or overall (all p-values $\geq$ .10).

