*2.4 Variables predictive of missingness.* Those with incomplete outcome data were more likely to be male (p=.05) and younger (p=.01), and have higher baseline BMI (p=0.03), greater highest weight (p=0.01), better weight quality of life at baseline (p=0.03) and lower food addiction at baseline (p=.03). Gender, age, and baseline BMI were already covariates in the models. We repeated the primary analyses to include the other three variables associated with missingness in the models and conclusions stayed the same.

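### No stated binge-remission model lists baseline binge frequency as a covariate; the test stays valid, but a modest amount of power may have been given up.

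*Combined protocol and SAP*

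**What the plan says.** Section 1.2 lists binge eating under the primary outcomes and defines two measures from the EDE interview. The first is a monthly binge frequency, which at baseline is averaged over the preceding three months. The second is remission: "Binge Remission was defined as zero binge episodes in the previous month". Section 1 describes who was recruited: "Potential participants were Veterans with recurrent binge eating seeking weight loss".

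Section 2 sends remission to logistic regression: "Logistic regression models were used for categorical outcomes such as binge remission and achieving clinically meaningful weight loss". The next sentence holds the only covariate list in the document: "The outcomes were transformed to approach normality as needed and models controlled for treatment, time, gender, age, and baseline BMI".

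Two re-runs with extra covariates are reported. Section 2.1 states: "All the analyses with cohort (categorical variable) added to the models were run and conclusions were substantively the same". Section 2.4 states: "We repeated the primary analyses to include the other three variables associated with missingness in the models and conclusions stayed the same". Those three variables are highest weight and the baseline scores for weight quality of life and food addiction. Baseline binge frequency appears in none of these models.

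The stratification factor is not listed for any model either. Section 1.6 gives it as: "Stratified randomization (clinical BED (n=101) and subclinical BED (n=8)) to the two conditions".

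The documents state no sample-size calculation, power, significance level or remission rate. They also do not say how strongly baseline frequency predicts later remission.

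**The concern.** In a randomised comparison, adjusting for a strong baseline predictor of the outcome raises power at no cost in validity. The baseline level of the same behaviour is the obvious candidate, and here it was already in the data.

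Remission is the outcome for which the omission matters most. Participants entered with recurrent binge eating, so remission at baseline should be absent in all or nearly all of them. A baseline remission value would therefore carry almost no information on severity. Baseline severity can enter the remission model only as a covariate.

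Randomisation does little to balance it in a single trial, because the only stratifier splits participants 101 to 8. What is at stake is some sensitivity to a treatment effect on remission, and the chance to see whether the reported odds ratio holds once baseline severity is taken into account.

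**Working it through.** **Inputs from the documents.** Total N = 40 + 69 = 109 (section 2.1), split about equally between arms (section 1.7). Applying the missing-outcome percentages in section 2.3:
- month 3: 109 × (1 − 0.119) = 96
- month 9: 109 × (1 − 0.193) = 88
- month 15: 109 × (1 − 0.248) = 82

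**Assumed inputs.** Two-sided 5% level; remission of 20% v 45% or 30% v 55%; prognostic strength of 0, 0.3, 0.6 or 1.0 log-odds per SD of baseline binge frequency. The plan has no power figure to reproduce.

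**Hand check of unadjusted power, 48 per arm.** Power = Φ[(Δ − 1.96·SE0)/SE1], where SE0 = √(2p̄(1 − p̄)/48) and SE1 = √((p1(1 − p1) + p2(1 − p2))/48).
- 20% v 45%: SE0 = √(0.43875/48) = 0.0956; SE1 = √(0.4075/48) = 0.0921; (0.25 − 0.1874)/0.0921 = 0.68; power 75%.
- 30% v 55%: SE0 = √(0.48875/48) = 0.1009; SE1 = √(0.4575/48) = 0.0976; (0.25 − 0.1978)/0.0976 = 0.53; power 70%.

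**Single-visit simulation.** N = 96, 4,000 replicates per cell, logistic regression on treatment, age, BMI and gender, without and then with baseline binge frequency. Power in %:

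| Log-odds per SD | 20% v 45% | Gain | 30% v 55% | Gain |
|---|---|---|---|---|
| 0 | 74.9 → 75.1 | 0.2 | 70.7 → 70.6 | −0.1 |
| 0.3 | 74.5 → 75.6 | 1.1 | 69.0 → 69.6 | 0.6 |
| 0.6 | 73.4 → 76.1 | 2.7 | 68.7 → 71.6 | 2.9 |
| 1.0 | 75.1 → 81.1 | 6.0 | 69.7 → 76.5 | 6.8 |

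The unadjusted column agrees with the hand check. The Monte Carlo standard error of each gain is at most 0.63 points. Repeat simulations of these cells gave gains of about 0 to 3 points up to 0.6 and about 5 to 8 at 1.0. Other assumed rates (20% v 40%, 25% v 50%, 30% v 50%, 30% v 60%) gave 3.1 to 3.6 points at an odds ratio of 0.5 per SD (0.69 log-odds), and 5.7 to 7.7 at 0.35 (1.05 log-odds).

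**Where the gain comes from.** At 1.0 log-odds per SD and 20% v 45%, the median log odds ratio moves from 1.24 to 1.50 and its standard error from 0.48 to 0.55. The ratio rises from 1.24/0.48 = 2.6 to 1.50/0.55 = 2.7. The standard error does not shrink; the conditional effect is larger.

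**Type I error.** With equal true rates of 30%, rejection was 4.8% to 6.1% (Monte Carlo SE about 0.35), with or without the covariate. Repeat runs gave between 4.5% and about 6.5% either way.

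**Three visits pooled.** This used 96, 88 and 82 observed, with a subject random-effect SD of 1 and a subject-clustered standard error, none of which the SAP specifies. For 20% v 45% and 30% v 55%, unadjusted power is already 92% to 96% and the gain is 0 to 5 points. For smaller differences (20% v 37%, 30% v 48%), unadjusted power is 67% to 75%. The gain there is about 0, 1 and 4 points at 0, 0.3 and 0.6, rising to about 9 to 12 at 1.0 (for example 70.3 → 80.9 and 66.8 → 79.1).

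**Chance imbalance at month 3.** The 95% range for the arm difference in baseline frequency is ±1.96 × √(2/48) = ±0.40 SD. At an assumed 0.6 log-odds per SD, that moves the log odds ratio by about ±0.6 × 0.40 = ±0.24.

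**Stratum.** With p = 8/109 = 0.073 and an assumed stratum difference of d SD, the reduction in SE from including it is 1 − 1/√(1 + p(1 − p)d²). This gives 0.2% at d = 0.25, 0.8% at d = 0.5 and 3.2% at d = 1.

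**The case against.** The omission itself is plain from the text. The case on the other side concerns how much it matters.

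- **The fix cannot repair the stated loss.** The SAP is written in the past tense and reports results. A post hoc model beside an unchanged main result restores no power to that result, and it estimates a different, conditional odds ratio. This stands.
- **The chosen covariates are defensible.** Under randomisation, adjusting for gender, age and baseline BMI without a further covariate gives a valid test. This stands. A reader might infer a biased comparison or an inflated error rate, but the type I error figures show neither.
- **Only one outcome is touched.** Section 2.3 gives the singular title of primary outcome to average monthly binges, which goes to a mixed model. Remission is defined under the primary-outcomes heading but has no precedence. This stands. A reader might infer the same loss for the mixed models, and the documents do not support that. Baseline is one of the visits ("Participant assessments were conducted by blind assessors at baseline, post-treatment (3-months), and 6- and 12-month follow-ups"), time is in the model, and section 2.2 says that every available observation is used. Baseline may therefore already be in those models as a response.
- **Every size is assumed, and the largest is the least supported.** This stands. A reader might quote 12 points, but that needs 1.0 log-odds per SD, smaller differences and a pooled model that the SAP does not describe.
- **Section 2.4 already shows insensitivity to the covariate set.** This stands in part. Food addiction and weight quality of life are related to severity but do not replace baseline binge frequency. Section 2.4 also does not say whether remission was among the analyses repeated.

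**Conclusion.** The point holds as a minor matter of efficiency, confined to binge remission. An available and plausibly prognostic baseline measure is missing from the stated model and from both sensitivity models. Under the month 3 assumptions above, the cost is most likely a few points of power, and it is zero if baseline frequency is not prognostic. The documents supply neither of the two quantities that fix its size, namely the remission rates and the strength of the association, so no single figure can be given.

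The missing stratum does not enlarge the point, because its effect on precision is very small with 8 of 109 participants subclinical. How baseline enters the mixed models, which treatment-by-time contrast was tested, and which look-back window defines binge frequency at follow-up are separate documentation matters. None of them bears on this conclusion.

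**What to change.** Add baseline binge frequency, log-transformed if skewed, to the binge-remission logistic model, and keep gender, age and baseline BMI. Label the analysis post hoc. Report its odds ratio beside the original and say that it is conditional on baseline frequency, so a value further from 1 is expected when the covariate is prognostic. Readers should compare the direction and the strength of evidence rather than the two odds ratios alone. The original model stays as the main result.

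Optionally, include the clinical v subclinical BED stratum in the continuous models so that the analysis matches the randomisation. It may be left out of the logistic model, since only 8 participants are subclinical.

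The cost is one extra fit on data already held, one more line in a results table and a sentence of explanation.

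### The listed model terms include neither the outcome's baseline value nor treatment-by-time, so as written the model cannot show whether a CBT effect lasts and is imprecise or distorted.

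*Combined protocol and SAP*

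**What the plan says.** Section 2 describes mixed-effects models for continuous outcomes and logistic regression for categorical ones, then gives a single list of terms for all of them: "models controlled for treatment, time, gender, age, and baseline BMI". Baseline BMI is the only baseline measurement in it apart from gender and age.

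Two later paragraphs describe added terms:

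- Section 2.1: "All the analyses with cohort (categorical variable) added to the models were run".
- Section 2.4: "We repeated the primary analyses to include the other three variables associated with missingness in the models". The three variables are highest weight, weight quality of life and food addiction.

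Neither adds baseline binge frequency, a baseline eating-pathology score or an interaction with time.

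Section 1.1 sets the assessments "at baseline, post-treatment (3-months), and 6- and 12-month follow-ups (9- and 15-months after randomization". Section 1.2 shows that a baseline value of binge frequency exists, defined as the "average number of monthly binge episodes for the past three months at baseline"; later visits use the past month only.

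The documents do not say which visits are response rows, how time is coded, or what covariance structure was used. Section 2.3 counts incompleteness over months 3, 9 and 15 only ("35.8% of subjects had incomplete outcome data (missing outcome at any of timepoints"). That fits a follow-up-only response at least as well as one that includes baseline, but does not settle it.

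**The concern.** CBT is given over three months and outcomes are then measured at months 3, 9 and 15. The two later visits are there to show whether any benefit persists. One treatment coefficient without an interaction cannot show that, whichever visits are responses.

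The baseline outcome raises a second problem, and its form depends on the response rows:

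- **Follow-up-only reading (months 3, 9, 15).** Randomization keeps the coefficient unbiased for an averaged effect. But a predictor already collected goes unused, so the interval is wider than it need be and the estimate moves with chance baseline differences. The plan checks balance ("Baseline characteristics were compared between the treatment groups using ANOVA and chi-squares as appropriate") but lists no adjustment for a chance difference in the outcome itself.
- **Baseline-row reading (baseline also a response).** The single coefficient mixes in a visit at which there is no true difference between arms, so in general it is not the effect at any follow-up visit.

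**Working it through.** The plan states no power, effect size, SD or correlation, so there is no design figure to reproduce.

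**Inputs from the documents**
- Randomized: 101 + 8 = 109 (section 1.6), about half to CBT (section 1.7).
- Missing at months 3, 9 and 15 (section 2.3): 11.9%, 19.3% and 24.8% of 109 = 13, 21 and 27, leaving 96, 88 and 82 observed.
- Incomplete at any visit: 35.8% of 109 = 39. These counts allow 533 overlap patterns; the ranges below cover all of them.

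**Assumptions, not in the documents**
- Arms of 54 and 55.
- Gaussian outcome, follow-up SD 1, equal correlation r between all visits after the listed covariates; r = 0.3, 0.5, 0.7.
- Missingness equal by arm and unrelated to outcome.

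**1. Durability.** With complete data and equal correlations, the follow-up-only coefficient is the mean of the three visit effects. A constant effect gives (0.50 + 0.50 + 0.50)/3 = 0.50 SD. A fading effect gives (0.75 + 0.50 + 0.25)/3 = 0.50 SD. The two cannot be told apart. With the stated missingness and r = 0.5, a fade of 0.6/0.4/0.2 SD returns 0.41–0.42 SD, the same as a constant effect of that size.

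**2. Precision, follow-up-only reading.** With complete data, ignoring the small cost of estimating the baseline slope:

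- Without baseline: Var = [(1 + 2r)/3] × (1/54 + 1/55)
- With baseline: Var = [(1 + 2r)/3 − r²] × (1/54 + 1/55)

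Here 1/54 + 1/55 = 0.0367. At r = 0.5 the SEs are √(0.6667 × 0.0367) = 0.156 and √(0.4167 × 0.0367) = 0.124.

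Generalised least squares with the stated missingness gives:

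| r | SE without baseline | SE with baseline | SE reduction | Equivalent extra participants |
|---|---|---|---|---|
| 0.3 | 0.149–0.151 | 0.137–0.139 | 8% | 18–19% |
| 0.5 | 0.163–0.168 | 0.132–0.134 | 20% | 55–57% |
| 0.7 | 0.176–0.182 | 0.112–0.115 | 36–37% | 144–152% |

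The gain depends on how well baseline predicts follow-up. With 0.5 between follow-ups, it is about 7% if the baseline–follow-up correlation is 0.3, and 3% if it is 0.2. With correlation decaying by visit (AR(1)) it is about 9% at 0.5 and 23–24% at 0.7.

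**3. Chance imbalance.** The SE of a baseline difference is √0.0367 = 0.192 SD. A difference of one SE shifts the unadjusted coefficient by r × 0.192 = 0.06, 0.10 or 0.13 SD.

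**4. Distortion, baseline-row reading.** The share of a constant effect that the coefficient returns is:

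- Working correlation 0: rows are weighted equally, so (96 + 88 + 82)/(109 + 96 + 88 + 82) = 266/375 = 71%.
- One random intercept and one residual variance: 66–71% for a working intraclass correlation from 0 to 0.9.
- Baseline variance half the follow-up variance and modelled separately: 42%, 28% and 1% at r = 0.3, 0.5 and 0.7.
- Baseline variance double and modelled separately: 89–90%, 98–99% and 116–118%.

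Size and direction therefore depend on a covariance structure that is not stated.

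**5. What a visit-specific model can deliver.** With baseline and treatment-by-visit at r = 0.5, the month 3 SE is about 0.176, against about 0.133 for the adjusted average. The SE of month 3 minus month 15 is 0.215–0.220, so power for a 0.4 SD fade is 44–46%. It is 34–35% at r = 0.3 and 65–67% at r = 0.7.

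**The case against.** The strongest reply is that the sentence is a covariate summary, not a model specification. It covers mixed and logistic models for every outcome, speaks of controlling for the very effect of interest, and omits the random effects that the same section says were used. An interaction may have been fitted and not mentioned. Baseline may even have been a response row with treatment-by-time, a common model in which baseline information enters through the response and no baseline covariate would be listed. This stands as a limit: the documents show what is listed, not what was fitted. It does not remove the point, because that model needs an interaction the list does not contain, and a reader cannot reconstruct it.

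Second, the follow-up-only reading is valid, and its efficiency loss rests on assumed correlations. That is right. Binge frequency gives reason to doubt the high end: its baseline window is three months against one later, and entry criteria restrict its baseline range. The window difference also favours using baseline as a covariate over a response row.

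Third, the distortion arises only under the reading with less textual support, and one scenario returns 98–99% of the effect. Also right: it is a conditional risk, not a demonstrated bias.

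The durability gap depends on none of these assumed values.

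**Conclusion.** The concern holds for the model as listed. Without treatment-by-time, no analysis in the plan can show whether an effect at month 3 is still present at months 9 and 15. Without the baseline outcome, the coefficient is either less precise than the data allow (SE reducible by roughly 3% to 37% over the correlations tried) or, if baseline is a response row, distorted by an amount and in a direction that the documents do not determine.

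Confidence is moderate, because the list may be incomplete. The figures assume a Gaussian outcome and missingness unrelated to outcome. They may not carry over to a transformed or count-type binge frequency, which the plan allows for ("Change of model type as well as transformation of the data were considered if model assumptions were not met"). They do not apply to percent weight loss, which already incorporates baseline weight, or to the logistic models. This should be fixed; it does not by itself invalidate the trial's comparison.

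**What to change.** State for each outcome which visits are response rows, how time is coded, the covariance structure, and whether treatment-by-time was fitted. Then, where the terms were absent:

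- **Eating pathology, binge frequency and questionnaire scores:** model months 3, 9 and 15 with treatment, categorical visit, treatment-by-visit, the baseline value of the same outcome, gender, age and baseline BMI. Report the baseline-adjusted average effect and each visit contrast with its interval, and say which one leads.
- **Percent weight loss:** add treatment-by-visit.
- **Binge remission:** add baseline binge frequency and report by visit.

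Label any refit as post hoc.

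If the terms were in fact fitted, the cost is a sentence of wording. If not, it is a re-run on data already collected, using about three degrees of freedom (one for baseline, two for the interaction). The drawback is that single-visit contrasts are less precise than the average and power to detect fading is limited, so visit results should be read as estimates with intervals, not as tests of whether the effect persists.

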### *1.7 Treatment Conditions*

#### MOVE! (Treatment-as-Usual)

All participants received VA's Weight Management Program, MOVE!, as administered at their site, without research staff involvement. MOVE! is an evidence-based behavioral weight management program that includes treatment procedures, clinical algorithms, patient and provider information, and instructional materials. The program was widely disseminated and implemented beginning in January 2006 [17]. The 60-minute groups cycle every 16 weeks and are led by trained and monitored MOVE! clinicians who are from the following disciplines: primary care, psychology, nutrition, and physical therapy. Clinicians utilize materials available in hard copy or on-line, and encourage the use of, but do not require or provide, food diaries. Due to the COVID-19 pandemic, MOVE! modalities offered for the present study were expanded to include VA's virtual MOVE! and TeleMOVE! programs. Virtual MOVE! involves synchronous delivery of MOVE! groups via VA Video Connect (i.e., telehealth). TeleMOVE! involves asynchronous delivery of MOVE! content via home-based technology and as needed clinician phone contact. Thus, MOVE! in the present study involved two cohorts: 1) **in-person** MOVE! (n=40), and 2) **virtual** MOVE! or TeleMOVE! (n=69).

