#### Brief, Clinician-led Cognitive-Behavioral Therapy for BED

One-half of participants received CBT in addition to MOVE!. The CBT was administered via 9 hourly individual sessions over a three-month treatment period. The treatment was led by a licensed clinical psychologist or social worker following a CBT for BED manual specifically developed for this project. Based upon a manual from previous studies [18, 19], the manual was adapted for the VA healthcare user population using iterative input from VA clinicians experienced with Veteran and eating disorder care, a Veteran Engagement Group paid to provide investigators with feedback about the design of Veteran research, and a Veteran who served as one of the study clinicians for this project. The most notable adaptions included person-first language, Veteran-centered examples, graphical representation of concepts, and writing at the seventh-grade reading level. Four clinicians received training from the Principal Investigator (PI; RM), feedback on videorecording of every session for clinicians' first two cases, feedback and adherence ratings of 10% of sessions thereafter, and weekly supervision from the PI (RM). Participants completed daily records of food intake and binge episodes, and these were reviewed and checked weekly by clinicians. The treatment consisted of three overlapping phases. The first phase involved building a collaborative therapeutic relationship, educating the patient about the diagnosis of BED and maintaining factors of binge eating, and utilizing

behavioral strategies (self-monitoring and goal setting and problem-solving to achieve structured patterning, timing and settings for eating). The second phase integrated cognitive skills such that patients learned to identify and challenge maladaptive thoughts and emotional triggers related to eating/restriction and weight/shape. The final phase focused on the maintenance of change and relapse prevention. Brief clinician-led CBT was conducted in-person before the onset of the COVID-19 pandemic and by phone after.

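### Randomisation was stratified by clinical versus subclinical BED, but no described model includes that stratum; adding it is a small, nearly free improvement

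*Combined protocol and SAP*

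**What the plan says.** Section 1.6 names one stratification factor: "Stratified randomization (clinical BED (n=101) and subclinical BED (n=8)) to the two conditions was performed with a computer-generated sequence". It does not say whether allocation was blocked within stratum.

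The opening paragraph of section 2 gives the covariates for the mixed models and the logistic models together: "models controlled for treatment, time, gender, age, and baseline BMI".

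Two re-analyses with extra covariates follow. Section 2.1 reports: "All the analyses with cohort (categorical variable) added to the models were run and conclusions were substantively the same". Section 2.4 takes baseline variables that predicted missingness and reports: "We repeated the primary analyses to include the other three variables associated with missingness in the models and conclusions stayed the same". Those three are highest weight, weight quality of life and food addiction.

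No section mentions clinical versus subclinical status as a model term or explains leaving it out. Section 2 also does not say whether the baseline value of an outcome is a covariate, part of the repeated outcome vector, or unused.

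**The concern.** A factor used to stratify randomisation normally belongs in the analysis, because stratifying changes the sampling behaviour of the treatment contrast. When arms are balanced within stratum, the stratum adds no variability to the treatment difference. A model without it still counts the between-stratum spread as residual noise, so the reported standard error is somewhat too large and the test somewhat conservative. The factor here is the diagnostic status of the disorder under treatment, and the primary outcomes are eating pathology and binge eating, so a link with outcome is plausible.

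The trial ran two rounds of covariate-adjusted re-analysis, and as described neither used the one variable that governed allocation. At stake are a little precision and the match between analysis and design, not the validity of the comparison.

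**Working it through.** The plan states no effect size, power or standard error, so there is no figure of its own to reproduce. The counts are consistent: 101 + 8 = 109 and 40 + 69 = 109. The missingness rates fit that total: 13/109 = 11.9%, 21/109 = 19.3%, 27/109 = 24.8%.

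**Inputs from the documents.** Stratum sizes 101 and 8 (section 1.6). About half of participants received CBT (section 1.7). Section 2.3: "Outcome was missing for 11.9% of subjects at month 3, 19.3% at month 9, and 24.8% at month 15".

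**Assumptions.** Within-stratum SD 1; stratum difference d of 0.5, 1 or 1.5 SD, constant over time; within-person correlation 0.5; 1:1 arms; two-sided 5% test.

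**Single visit, all 109 observed, no baseline outcome.** Variance due to the stratum is v = (8/109)(101/109)d² = 0.0680d². The standard error falls by 1 − 1/√(1+v). With arms balanced within stratum, a test that omits the stratum has true error rate 2Φ(−1.96√(1+v)). The equivalent number of extra participants is 109v.

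| d | v | SE reduction | Error rate, stratum omitted | Equivalent extra participants |
|---|---|---|---|---|
| 0.5 | 0.0170 | 0.8% | 4.8% | 1.9 |
| 1 | 0.0680 | 3.2% | 4.3% | 7.4 |
| 1.5 | 0.1530 | 6.9% | 3.5% | 16.7 |

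For an assumed 0.5 SD treatment effect, power is 74.2% with the stratum and 73.7%, 72.1% and 69.3% without it.

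**Repeated visits: the answer depends on how baseline is used.** The mean number of observed post-baseline visits is 0.881 + 0.807 + 0.752 = 2.44. The within-stratum variance of a participant's post-baseline mean is then about 0.5 + 0.5/2.44 = 0.705.

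- *Post-baseline visits only, no baseline outcome.* The SE ratio is √(0.705/(0.705+v)), a reduction of 1.2%, 4.5% and 9.4%. Simulated random-intercept models with the stated missingness (3,000 trials each) gave 1.2%, 4.5% and 9.5%. Error rates with the stratum omitted were 4.7%, 4.0% and 3.3%. Under a true zero effect the mean estimate was within 0.003 SD of zero with or without the stratum.
- *Baseline outcome as covariate.* With the stratum, the residual variance is 0.705 − 0.5² = 0.455. Without it, the variance is 0.705 + v − (0.5+v)²/(1+v) = 0.459, 0.471 and 0.488. The SE reduction is 0.5%, 1.7% and 3.5%; simulation (300 trials each) gave 0.5%, 1.6% and 3.5%.
- *Baseline in the outcome vector, treatment-by-time contrast.* A constant stratum gap cancels in change from baseline. Simulation (300 trials each) gave 0.01%, 0.03% and 0.06%. This case does not apply to percent weight loss, which has no baseline value.

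**If allocation was not blocked within stratum.** One standard error of chance imbalance shifts a single-visit estimate without baseline adjustment by √(0.068 × 2/54.5) × d = 0.025, 0.050 and 0.075 SD. This averages to zero over randomisations.

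**Logistic models.** Separation arises if all observed subclinical participants share one result, which has probability p⁸ + (1−p)⁸. At assumed remission rates of 20%, 30% and 50% this is 17%, 6% and 0.8%. At month 15 about 8 × 0.752 = 6 would be observed, and the probabilities become 26%, 12% and 3%.

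**The case against.** The strongest reply is that this hardly matters. Only 8 of 109 participants are subclinical. The larger gains need a 1.5 SD stratum difference, for which the documents offer no support, and a model that ignores the baseline outcome. Section 1.1 lists a baseline assessment and section 1.2 defines baseline binge frequency, so the models may well use it; in a change-from-baseline contrast the stratum then does almost nothing. The conservatism also requires balance within stratum, which section 1.6 does not establish. A stratum this small can reasonably be left out of a logistic model, and one line of rationale in the covariate list would have answered most of the point.

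All of that stands as a limit on size, and it is why the range must start at zero. It does not remove the gap between sections 1.6 and 2: no rationale is given, and the adjustment costs one degree of freedom in the continuous models. It is also fair to say that the covariate list may be a summary. The text does not show that the stratum was excluded, only that it is not listed.

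A reader might infer that the omission biases the treatment effect or invalidates the comparison. Nothing in the documents supports this. Allocation was random, the omission does not shift the estimate on average, and with balanced strata the error runs towards caution.

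**Conclusion.** The point holds as a small improvement. The one stratification factor is absent from the main, cohort and missingness models as described. The reduction in standard error from including it runs from essentially zero, through about 0.5% to 4%, to about 1% to 10%, according to how the baseline outcome enters. These figures rest on assumed stratum differences of 0.5 to 1.5 SD, constant over time, and a within-person correlation of 0.5. Conclusions are unlikely to change.

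A reader might also want to fault section 2.1 for implying that CBT works equally well in the in-person and remote cohorts. A cohort covariate would not show that, but section 2.1 claims only that conclusions were substantively unchanged. There is no assertion of equal effects to correct, so this is not part of the point.

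**What to change.** In the mixed models for continuous outcomes, add BED stratum (clinical or subclinical) as a fixed covariate. Report the result beside the existing estimates, not in place of them, and label it as added after the original analyses.

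In the logistic models, use the stratum only as a sensitivity analysis, for example with Firth penalisation.

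If the stratum was already in the models, add it to the covariate list in section 2; nothing further is needed. Stating there how the baseline outcome enters would also let a reader judge what the adjustment can gain.

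The cost is one model degree of freedom and one labelled re-run on data already held, the same kind of work as the re-analyses in sections 2.1 and 2.4.
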